10.2.2. Protocol Defined Schedule of Events in PART B (Cohorts 4-6)

Procedure	Screening (Up to 28 days before Day 1)	Study Period (Days)													Follow-up (14-21 days post last dose) / Early Withdrawal	Notes	
		-2	-1	1	2	3	4	5	6	7	8	9	10	11	12		
Outpatient Visit	X															X	
Admission to Clinical Unit		X															
Inpatient Stay at Clinical Unit				←=====X=====→													
Discharge from Clinical Unit																X	Following completion of all assessments.
Informed Consent	X																
Inclusion and Exclusion Criteria	X																
Demography	X																
Full Physical Examination	X																Additional exams/screens may be performed, or brief exams made full exams, by the Investigator, as deemed necessary (e.g. where safety or laboratory findings indicate). Tests will be conducted within site specified standards.
Brief Physical Examination			X	X				X					X	X			
Drug/Alcohol/Smoki ng Screen	X		X														Tests include alcohol breath test, smoking breath test and urine drug screen.
Medical/Medication/ Drug/Alcohol History	X																
HIV, Hepatitis B and C Screening	X																
FSH + Oestradiol	X																Females only, if required
Holter Monitoring (48 hour)	X																

Procedure	Screening (Up to 28 days before Day 1)	Study Period (Days)													Follow-up (14-21 days post last dose) / Early Withdrawal	Notes	
		-2	-1	1	2	3	4	5	6	7	8	9	10	11	12		
Haem/Chem/ Urinalysis Test (Include Liver Chemistries)	X		X		X		X		X		X		X		X	X	If trace protein is detected, a repeat test can be performed. Sample to be drawn pre-dose on Days 2, 4, 6, 8 and 10. Non-fasted samples can be collected on Day -1 and Follow-Up Visit. All other samples to be collected in fasted state.
Cortisol Test			X										X				Tests to be performed in the early morning on Day -1 and Day 11. If levels are <420 nmol/L, then a ACTH stimulation test will be performed to assess hypothalamic pituitary adrenal (HPA) axis.
Safety biomarkers (KIM1, NGAL, Urinary albumin)				X				X									First urine sample of the morning to be collected (pre-dose). Additional samples may be collected, as deemed necessary by the Investigator (e.g. where safety or laboratory findings indicate).
Telemetry				X	X												Continuous at least 24 hr post-evening dose. Initiate at least 15 min. prior to dosing.
Randomization				X													
Study Treatment				X	X	X	X	X	X	X	X	X	X				BID dosing: GSK3186899 or placebo will be administered using a 12hr dosing interval. If a different dosing regimen is used, refer to Appendix 5 of Protocol.

Procedure	Screening (Up to 28 days before Day 1)	Study Period (Days)													Follow-up (14-21 days post last dose) / Early Withdrawal	Notes	
		-2	-1	1	2	3	4	5	6	7	8	9	10	11	12		
12-Lead ECG	X		X	T	X		X		X		X		X		X	X	Vital signs to include HR, BP, temperature and respiration rate. BP will be conducted in both a supine and standing position if participant develops any signs/symptoms which in the investigators opinion are suggestive of adrenal insufficiency. 12-Lead ECG and Vital Signs to be conducted on Day-1 and pre-dose Day 1 and then at the subsequent time points post first-dose: 30 min, 1 hr, 1.5hr, 2hr, 2.5hr, 4hr, 6hr, 13hr and 14hr For Days 2-10: pre-dose assessments only. Timings will be reviewed as cohorts progress and may be adjusted to ensure appropriate measurements relative to peak concentrations for subsequent cohorts If a different dosing regimen is used, refer to Appendix 5 for alternative ECG and Vital Signs time-points. T = Triplicate (for all assessments except temperature and respiratory rate). If any abnormal ECG reading is recorded, refer to Section Error! Reference source
Vital signs	X		X	T	X	X	X	X	X	X	X	X	X	X	X	X	

Procedure	Screening (Up to 28 days before Day 1)	Study Period (Days)													Follow-up (14-21 days post last dose) / Early Withdrawal	Notes	
		-2	-1	1	2	3	4	5	6	7	8	9	10	11	12		
																	not found. of protocol for appropriate action.
PK Blood sampling																	
PK samples will be collected pre-dose and at the following time points post first-dose:
 
Day 1: 10min, 30min, 1hr, 1.5hr, 2hr, 2.5hr, 3hr, 4hr, 5hr, 6hr, 8hr, 10hr, and 12hr
 
Days 2 – 9: Pre-dose PK samples collected for each dose
 
Day 10: PK samples will be collected pre-dose and at the following time points post first-dose: 10min, 30min, 1hr, 1.5hr, 2hr, 2.5hr, 3hr, 4hr, 5hr, 6hr, 8hr, 10hr, and 12hr.
 
The time points stated may be modified depending on emerging SAD PK profiles. If a different dosing regimen is used, refer to Appendix 5 of Protocol for alternative PK blood sampling time-points.
 
Blood volumes to be collected include:
 
 • 2 mL for post-dose 0-11 hrs, and • 5 mL for post-dose 12-24 hrs (Days 1 and 10).
Urine Sampling (metabolism)													X	X			A urine sample will be taken pre-dose (approx. 20mL). All urine from each participant will be collected from 0-24 hrs post dosing. Details of urine collection and processing are described in the SRM.

Procedure	Screening (Up to 28 days before Day 1)	Study Period (Days)													Follow-up (14-21 days post last dose) / Early Withdrawal	Notes	
		-2	-1	1	2	3	4	5	6	7	8	9	10	11	12		
Meals		X	X	X	X	X	X	X	X	X	X	X	X	X	X		
If on fed regimen: On Day 1 through to D10, participants will receive an adapted standard meal 30 mins prior to dosing.
 
If on fasted regimen: On Day 1 through to D10, participants will have fasted 8hr overnight prior to dose 1. A breakfast will be served approximately 2hr after dose 1. Dinner will be served at least 2hr prior to dose 2. A snack may be consumed approximately 2hr after dose 2.
 
Participants will receive standardized meals scheduled at the same time in each period. If a different dosing regimen is used, refer to Appendix 5 for alternative meal times.
 
Meals will be served as per the site schedule on Days -1 and Days 11-13.
 
Water permitted on an ad lib basis up to 1hr before dosing. No water to be taken in the hour prior to dosing except for the liquid part of the adapted standard breakfast for the Fed regimen.
 
At least 8 fl oz (240ml) to be taken 1 hour after dosing No water to be taken in the hour after dosing except for the rinse of the dose.

AE review		<=====X=====>													X		

Procedure	Screening (Up to 28 days before Day 1)	Study Period (Days)													Follow-up (14-21 days post last dose) / Early Withdrawal	Notes	
		-2	-1	1	2	3	4	5	6	7	8	9	10	11	12		
SAE review	X							X								X	
Concomitant medication review	X							X								X	

- The timing and number of planned study assessments, including safety, pharmacokinetic or other assessments may be altered during the course of the study based on newly available data (e.g., to obtain data closer to the time of peak plasma concentrations) to ensure appropriate monitoring.

Any changes in the timing or addition of time points for any planned study assessments must be documented and approved by the relevant study team member and then archived in the sponsor and site study files, but will not constitute a protocol amendment. The IRB/IEC will be informed of any safety issues that require alteration of the safety monitoring scheme or amendment of the informed consent form (ICF).

10.3. Appendix 3: Assessment Windows

10.3.1. Definitions of Assessment Windows for Analyses

Nominal time will be used for all analysis except PK analysis where planned and actual time will be used.

10.4. Appendix 4: Study Phases and Treatment Emergent Adverse Events

10.4.1. Study Phases

For each period in Part A Cohorts 1, 2 and 3, assessments and events will be classified according to the following phases:

Study Phase	Definition
Pre-Treatment	Date and time < Study Treatment Start Date and time of each period
Treatment	Study Treatment Start Date and time ≤ Date and time ≤ Study Treatment End Date and time + 24 hours, in each period
Post-Treatment	Date and time > Study Treatment End Date and time + 24 hours, within each period

Note: Estimated half-life of GSK3186899 is approx. 1.3 hours. The maximum of (5 half-lives (~ 6.5 hours) and 24 hours) after the Study Treatment End Date and time have been considered to define the end of treatment phase. If half-life is longer than 5 hours, then the definition will be revised accordingly.

Post-treatment phase will additionally include any events occurring in the washout period before start of the next treatment dose.

For the interim, the start of the period will be defined from the first dose of the period and then the end of the period is just before the first dose in the next period. For the final period the end date is just before the withdrawal/follow up visit.

For Part B Cohorts 4, 5 and 6, assessments and events will be classified according to the following:

Study Phase	Definition
Pre-Treatment	Date < Study Treatment Start Date of each Cohort
Treatment	Study Treatment Start Date and time ≤ Date and time ≤ Study Treatment End Date and time + 24 hours, in each cohort
Post-Treatment	Date and time > Study Treatment End Date and time 24 hours, in each cohort

Note: Estimated half-life of GSK3186899 is approx. 1.3 hours. The maximum of (5 half-lives (~ 6.5 hours) and 24 hours) after the Study Treatment End Date and time have been considered to define the end of treatment phase. If half-life is longer than 5 hours, then the definition will be revised accordingly.

10.4.1.1. Study Phases for Concomitant Medication

Study Phase	Definition
Prior	If medication end date is not missing and is before to the screening visit
Concomitant	Any medication that is not a prior

NOTES:

- Please refer to [Appendix 7: Reporting Standards for Missing Data](#) for handling of missing and partial dates for concomitant medication. Use the rules in this table if concomitant medication date is completely missing.

10.4.2. Treatment Emergent Flag for Adverse Events

Flag	Definition
Treatment Emergent	
• If AE onset date is on or after treatment start date and time, it is considered as treatment emergent• For Part A, if AE onset is during one period and worsens during a later period it would be counted in both periods.
◦ For the initial period the logic would be as above.◦ For the later period the logic would use the treatment dates associated with the later period: Treatment Period Start Date \leq AE Worsening Date \leq Study Treatment Stop Date

NOTES:

- If the study treatment stop date is missing, then the AE will be considered as On-Treatment.
- Time of study treatment dosing and start/stop time of AEs should be considered, if collected.

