### Study Duration of Cohorts 1-3

Screening	All screening assessments to be completed within 28 days prior to first-dose.
Treatment Period	Cohorts 1 and 2 will comprise of 4 treatment periods, investigating 4 dosing regimens under fasted conditions. Cohort 3 will comprise of 2 treatment periods, investigating 2 dosing regimens under fasted and fed conditions.  Each regimen will consist of a single dose given on Day 1, with participants in-house for 4 nights and 5 days. Participants will be admitted to the unit the day before dosing (Day -1) and will remain in the unit overnight until Day 4, when they will be discharged after completion of all assessments.
Washout Period	At least 10 days between each dose for an individual participant.
Follow-up	At least 14 days and no greater than 21 days after last study drug administration. If warranted, additional follow-up visits may be scheduled.
Total duration	Cohorts 1 and 2 will be approximately 11-12 weeks each Cohort 3 will be approximately 8-9 weeks

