**Table 1 Study Duration of Cohorts 1-3**

Screening	All screening assessments to be completed within 28 days prior to first-dose.
Treatment Period	Cohorts 1 and 2 will comprise of 4 treatment periods, investigating 4 dosing regimens under fasted conditions. Cohort 3 will comprise of 2 treatment periods, investigating 2 dosing regimens under fasted and fed conditions.  Each regimen will consist of a single dose given on Day 1, with participants in-house for 4 nights and 5 days. Participants will be admitted to the unit the day before dosing (Day -1) and will remain in the unit overnight until Day 4, when they will be discharged after completion of all assessments.
Washout Period	At least 10 days between each dose for an individual participant.
Follow-up	At least 14 days and no greater than 21 days after last study drug administration. If warranted, additional follow-up visits may be scheduled.
Total duration	Cohorts 1 and 2 will be approximately 11-12 weeks each Cohort 3 will be approximately 8-9 weeks

[figure not shown]

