2.3. Study Design

Overview of Study Design and Key Features		
Figure 1 Study Design (Part A)		
Screening Period (28 days prior to D1)	Treatment Period	Follow-up Period (7-14 days post last dose)
Cohort 1 N = 8 (6A:2P)	DL1 → DL2 → DL3 → DL4 → 	
Cohort 2 N = 8 (6A:2P)	DL4 → DL5 → DL6 → DL7 → 	
Cohort 3 N = 14 (14A)	DLX →  DLX-FD → 	

All doses are fasted unless otherwise specified
 
♦ = Dose escalation meeting ◆ = Safety data review meeting
		
DL = Dose level; DLX = Dose level to be determined; FD = Fed Conditions; A = Active; P = Placebo		
Figure 2 Study Design (Part B)		
Screening Period (28 days prior to D1)	Treatment Period	Follow-up Period (7-14 days post last dose)
Cohort 4 N = 8 (6A:2P)	Repeat DL1 10 days → 	
Cohort 5 N = 8 (6A:2P)	Repeat DL2 10 days → 	
Cohort 6 N = 8 (6A:2P)	Repeat DL3 10 days → 	

♦ = Dose escalation meeting
 
DL = Dose level; A = Active; P = Placebo
 
Note: DL7 was not dosed in the study due to higher than expected exposures.
		
Design Features	
This study will be a randomized, double-blind (sponsor unblinded), placebo-controlled, 2-part study of the oral administration of GSK3186899A in healthy participants.
 
Planned to include approximately 54 participants and will consist of 2 parts as below:
 
 Part A will include a single-ascending, sequential crossover design in up to 3 cohorts of participants (Cohorts 1, 2 and 3). Part A Cohorts 1-2 will comprise of a 4 period crossover which includes 4 dosing regimens under fasted conditions. Part A Cohort 3 will comprise of a 2 period crossover which includes 1 dosing regimen 	

Overview of Study Design and Key Features	
	
under fasted conditions and 1 regimen under fed conditions. The fed conditions regimen will investigate the safety, tolerability and PK of a single dose of GSK3186899 following food administration.
 
 Part B will be a twice-daily (BID) 10-day repeat dose design in up to 3 parallel cohorts of participants (Cohorts 4, 5 and 6). Part B may include drug administration after either fed or fasted conditions, this will be dependent on the interim results from Part A. If under fasted conditions, participants will be required to fast at least 2 hours before and after drug administration.

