10.12.5. Safety Tables

Safety: Tables					
No.	Population	IDSL / Example Shell	Title	Programming Notes	Deliverable
Adverse Events (AEs)					
3.1.	Safety	AE1CP	Summary of All Adverse Events by System Organ Class and Preferred Term – Part A	ICH E3	IA, SAC
3.2.	Safety	AE1	Summary of All Adverse Events by System Organ Class and Preferred Term – Part B	ICH E3	SAC
3.3.	Safety	AE3	Summary of Common (>=5%) Adverse Events by Overall Frequency – Part A	FDAAA, EudraCT	SAC
3.4.	Safety	AE3	Summary of Common (>=5%) Adverse Events by Overall Frequency – Part B	FDAAA, EudraCT	SAC
3.5.	Safety	AE1	Summary of All Drug Related Adverse Events by System Organ Class and Preferred Term – Part A	ICH E3	SAC
3.6.	Safety	AE1	Summary of All Drug Related Adverse Events by System Organ Class and Preferred Term – Part B	ICH E3	SAC
Serious and Other Significant Adverse Events					
3.7.	Safety	AE16	Summary of Serious Adverse Events by System Organ Class and Preferred Term (Number of Subjects and Occurrences) – Part A	FDAAA, EudraCT	SAC
3.8.	Safety	AE16	Summary of Serious Adverse Events by System Organ Class and Preferred Term (Number of Subjects and Occurrences) – Part B	FDAAA, EudraCT	SAC
Laboratory: Chemistry					
3.9.	Safety	LB1	Summary of Chemistry Changes from Baseline – Part A	ICH E3	SAC
3.10.	Safety	LB1	Summary of Chemistry Changes from Baseline – Part B	ICH E3	SAC

Safety: Tables					
No.	Population	IDSL / Example Shell	Title	Programming Notes	Deliverable
3.11.	Safety	LB17	Summary of Worst-Case Chemistry Results by PCI Criteria Post-Baseline Relative to Baseline – Part A	ICH E3	SAC
3.12.	Safety	LB17	Summary of Worst-Case Chemistry Results by PCI Criteria Post-Baseline Relative to Baseline – Part B	ICH E3	SAC
Laboratory: Haematology					
3.13.	Safety	LB1	Summary of Haematology Changes from Baseline – Part A	ICH E3	SAC
3.14.	Safety	LB1	Summary of Haematology Changes from Baseline – Part B	ICH E3	SAC
3.15.	Safety	LB17	Summary of Worst-Case Haematology by PCI Criteria Post-Baseline Relative to Baseline – Part A	ICH E3	SAC
3.16.	Safety	LB17	Summary of Worst-Case Haematology by PCI Criteria Post-Baseline Relative to Baseline – Part B	ICH E3	SAC
Laboratory: Urinalysis					
3.17.	Safety	LB1	Summary of Urine Concentration Changes from Baseline – Part A	ICH E3 Includes Baseline values.	SAC
3.18.	Safety	LB1	Summary of Urine Concentration Changes from Baseline – Part B	ICH E3 Includes Baseline values.	SAC
3.19.	Safety	UR3a	Summary of Urinalysis Dipstick and Microscopy Results – Part A		SAC

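### Part A adverse event counts have no common window: each cohort's final, highest-dose period is observed for 14-21 days, earlier periods for as little as 10

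*SAP*

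**What the plan says.** - **Treatment-emergent rule (SAP 10.4.2).** "If AE onset date is on or after treatment start date and time, it is considered as treatment emergent". The only upper limit in that section concerns an AE that carries over and worsens in a later period; onset has none.
- **Study phases (SAP 10.4.1).** Each Part A period has a treatment phase from dosing to 24 hours after it. The post-treatment phase that follows takes in the washout up to the next dose. For the interim, a period ends just before the next period's first dose, and "For the final period the end date is just before the withdrawal/follow up visit".
- **Spacing and follow-up (Protocol, Study Duration of Cohorts 1-3).** The washout row requires "At least 10 days between each dose for an individual participant". The closing visit is then set at "At least 14 days and no greater than 21 days after last study drug administration". Protocol 9.2.1 collects AEs up to the follow-up visit.
- **Dose order (Protocol 5.1, SAP 2.3).** Cohort 1 is planned for dose levels (DL) 1 to 4 and Cohort 2 for DL4 to DL7, in ascending order, with 6 active and 2 placebo doses per period. The SAP notes that DL7 was not dosed.
- **Displays (SAP 10.12.5).** Table 3.1 is titled "Summary of All Adverse Events by System Organ Class and Preferred Term" for Part A. Neither it nor Tables 3.3 and 3.5 names a phase or window.
- **Laboratory draws (Protocol 2.1).** Scheduled post-dose draws fall on Day 2 and Day 4 of each period, plus one at follow-up. SAP 10.6.1 mentions a summary row covering any visit after baseline and extends that convention to the tables of potential clinical importance.
- **Conflicting follow-up length.** SAP Figures 1 and 2 label follow-up "Follow-up Period (7-14 days post last dose", against 14-21 days in SAP Appendix 2 and the protocol.

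**The concern.** Safety by dose is the primary objective, and the final tables will set the dose levels and placebo side by side. If one column is observed for longer than its neighbours, background events accumulate there and can pass for a drug effect. Within each cohort the longer window falls on the highest active dose level, where a reader is most ready to see a signal. With six active participants per dose level and period, one extra participant with an AE is 17% of the group. The SAP defines an equal 24-hour phase, but no listed Part A AE table says it uses that phase.

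**Working it through.** **1. Reproduce the stated durations.** Inputs from Protocol Table 1: screening ("All screening assessments to be completed within 28 days prior to first-dose"), the 10-day minimum gap and follow-up at 14-21 days.

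- Cohorts 1-2: 28 + 3 × 10 + 14 to 21 = 72 to 79 days = 10.3 to 11.3 weeks, or 11-12 rounded up.
- Cohort 3: 28 + 10 + 14 to 21 = 52 to 59 days = 7.4 to 8.4 weeks, or 8-9 rounded up.

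The protocol says "Cohorts 1 and 2 will be approximately 11-12 weeks each Cohort 3 will be approximately 8-9 weeks", so the minimum gap is consistent with the plan. Taken without rounding, with full 28-day screening, the Cohort 1-2 totals imply (77 − 28 − 14)/3 = (84 − 28 − 21)/3 = 11.7 days between doses. Pairing 84 days with 14-day follow-up gives 14 days.

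**2. AE window by dose level, 10-day gaps.**

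- DL1-3 and DL5-6 (never in a planned final period): 10 days.
- DL4 (6 doses in Cohort 1's final period, 6 in Cohort 2's first): (6 × 14 + 6 × 10)/12 = 12.0 to (6 × 21 + 6 × 10)/12 = 15.5 days.
- DL7 as planned: 14-21 days.
- Pooled placebo (4 of 16 doses in a final period): (12 × 10 + 4 × 14)/16 = 11.0 to (12 × 10 + 4 × 21)/16 = 12.75 days.

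**3. Sensitivity to the actual gap.**

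| Gap (days) | DL4 | Final period | Pooled placebo | Final / earlier | Final / placebo |
|---|---|---|---|---|---|
| 10 | 12.0-15.5 | 14-21 | 11.0-12.75 | 1.40-2.10 | 1.27-1.65 |
| 11.7 | 12.8-16.3 | 14-21 | 12.25-14.0 | 1.20-1.80 | 1.14-1.50 |
| 14 | 14.0-17.5 | 14-21 | 14.0-15.75 | 1.00-1.50 | 1.00-1.33 |

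With the 7-14 days of the SAP figures and a 10-day gap, final / earlier is 0.70-1.40, so the direction could reverse.

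**4. If Cohort 2 ended at DL6 (assumption).** 800 mg then has 14-21 days and 600 mg has 10. Pooled placebo becomes (10 × 10 + 4 × 14)/14 = 11.1 to (10 × 10 + 4 × 21)/14 = 13.1 days, and 800 mg against placebo is 1.26-1.60.

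**5. Effect on AE counts with no drug effect.** P(at least one AE) = 1 − exp(−rate × days). The rates are assumptions; the documents give none.

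| Rate per day | 10 days | 14 days | 21 days |
|---|---|---|---|
| 0.005 | 4.9% | 6.8% | 10.0% |
| 0.02 | 18.1% | 24.4% | 34.3% |
| 0.03 | 25.9% | 34.3% | 46.7% |

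At 0.02 per day, the expected number out of 6 participants is 1.09, 1.47 and 2.06: an excess of 0.38 to 0.97 of a participant.

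**6. Laboratory values, if the follow-up draw counts.** The last period has 3 scheduled post-dose draws against 2. At an assumed 5% flag chance per independent draw: 1 − 0.95² = 9.8% against 1 − 0.95³ = 14.3%. At 2.5% the figures are 4.9% and 7.3%; at 10%, 19.0% and 27.1%. The follow-up sample may also be non-fasted, whereas Day 2 and Day 4 samples are fasted and the SAP 10.8.1 glucose limit (above 5.8 mmol/L) is labelled fasted.

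**7. After the fix.** A 240-hour cap gives every column 10 days (ratio 1.00), and Day 2 plus Day 4 gives two draws per period.

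**The case against.** A reader might infer that safety counts rise with dose by construction. They do not: the planned window is flat apart from a step in each cohort's final period, and DL4 has a longer average window than DL5 or DL6. Four further points stand at least in part.

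- **Ten days is a minimum.** Longer actual gaps shrink the imbalance, and 14-day gaps with follow-up at day 14 remove it. Placebo also shares the final periods, so the contrast with placebo is smaller than that with earlier doses.
- **It is tempting to say that every 800 mg exposure has the long window.** The SAP says only that DL7 was not dosed, and Protocol 8.1.1 lets the team use remaining periods for lower or repeated doses. If Cohort 2 had a fourth period, the long window falls on whatever was given then.
- **The laboratory effect is not established.** The SAP wording on post-baseline visits suggests that the follow-up draw counts but does not say so, and the interim definition of the final period would exclude it. Draws within one person are not independent, so the percentages are only illustrative. For vital signs, follow-up adds one reading to ten scheduled post-dose time points, which is negligible.
- **The consequence is limited.** The analysis is descriptive. Escalation decisions need at least 48 hours of post-dose data and use no Biostatistics displays. The half-life is estimated at about 1.3 hours, and events soon after dosing are captured equally in every period. All AEs are listed, and the standard display shells, which might set a window, are not reproduced in the SAP.

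None of this supplies a common window for the final AE tables by treatment. Cohort 3 adds nothing to a dose comparison: it tests one dose level, with participants randomized to fed or fasted.

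**Conclusion.** The concern holds for Part A Cohorts 1-2. Followed as written, the SAP counts AEs for longer in each cohort's final, highest-dose period than in earlier periods: 1.4-2.1 times as long at the minimum gap, 1.0-1.5 times with 14-day gaps, and about 1.27-1.65 times the pooled placebo window at the minimum gap. The excess concerns late background events. At an assumed 0.02 AEs per day it is up to about one participant in six. These figures rest on follow-up at 14-21 days and on the planned periods. A 600 versus 800 mg imbalance arises only if Cohort 2 ended at DL6. The laboratory asymmetry of three draws against two depends on a convention that the SAP leaves open. The documents do not support a steady dose trend in window length. This is a cheap improvement to a primary safety display, not a flaw that invalidates the analysis.

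**What to change.** - **AE tables.** In SAP 10.4.2 and the final Part A AE tables by treatment, add a count over one common window: onset from dosing to 240 hours after that dose, or to the next dose if sooner. Put later events in a separate follow-up column and in the listings, and keep the all-AE total.
- **Worst-case laboratory tables (3.11, 3.15, 3.21).** Derive the worst value by treatment from the Day 2 and Day 4 draws common to every period, and show follow-up as its own row.
- **Follow-up length.** Reconcile the 7-14 days in SAP Figures 1 and 2 with the 14-21 days in SAP Appendix 2 and the protocol.

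The cost is SAP wording and one window flag in programming, with no change to conduct or data collection. The downside is that late events sit in a separate column beside the dose column, although all remain reported. The 24-hour treatment phase would also equalise the windows, but it leaves out most of the observation time that every period shares.
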